Q1. What is the lung deposition behaviour of inhaled bronchodilator aerosols of different particle size within the airways of patients with chronic obstructive pulmonary disease (COPD)? How does this distribution compare to that observed in healthy subjects with no lung disease?

Q2. What is the effect of different patient inhalation flows on the lung deposition of different sized bronchodilator particles? Is there a specific particle size and inhalation flow to achieve optimal lung deposition in COPD patients?

Q3. Does the regional deposition and distribution of inhaled bronchodilator aerosols influence the clinical (physiological pharmacodynamic) and systemic (urinary pharmacokinetic) responses in COPD patients?

3. Study Design

This protocol has two studies: Lung DEPOSITION study (in COPD patients and Healthy subjects) and Lung PHYSIOLOGY study (in COPD patients and Asthmatics).

Each study (Lung DEPOSITION and Lung PHYSIOLOGY) will be a randomised, double-blind, cross-over study (6 monodisperse 'fine-mist' aerosol treatments, controlled against one polydisperse 'coarse-mist' pressurised metered dose inhaler (pMDI) visit). Treatments will be given as one-off dose-administration. There will be an interval of at least 5 days between each study visit.

The Lung DEPOSITION study will involve radiolabelled drug treatments (monodisperse aerosols only = 6 visits). All the treatments in the LUNG PHYSIOLOGY study will be non-radiolabelled.

4. Study Outcomes

Primary outcome:

Lung DEPOSITION study: The primary endpoint for aerosol deposition is penetration index (PI) calculated from planar-images, which will indicate differences in regional lung deposition as a function of particle size.

Lung PHYSIOLOGY study: The primary endpoints are multi-breath nitrogen washout (MBNW) indices of acinar airways (Sacin) and conducting airways (Scond), which will indicate differences in small (and large) airway physiology as a function of particle size.

Secondary outcomes:

The secondary outcome measures for both studies are: analysis of the lung physiology (MBNW, Impulse oscillometry (IOS), spirometry, body plethysmography) and urine pharmacokinetics (urine 0-30minutes, 0-24 hours, 30mins -24 hours)

5. Study Centre / Number of Patients / Recruitment

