The single-centre study will be carried out at the Asthma Lab, Royal Brompton Hospital and National Heart and Lung Institute, London, UK. Patients will be recruited from: Asthma Lab NHLI, Respiratory outpatients of the Royal Brompton and Harefield NHS Foundation Trust, St Mary's Hospital part of Imperial College NHS Trust, Local GP Practices and from our current patient Asthma Lab database from local GP Practices.

The study will recruit;

Lung DEPOSITION study: 12 mild-moderate COPD patients, 12 healthy subjects

Lung PHYSIOLOGY study: 26 mild-moderate COPD patients, 13 mild-moderate asthmatic patients

6. Inclusion criteria

COPD patients, either male or female, over the age of 40 with a clinical diagnosis of COPD with airflow obstruction (FEV1/FVC<0.7) and post-bronchodilator FEV1>50% predicted, gas trapping (on lung volume testing), and decreased carbon monoxide transfer factor.

Healthy subjects will be non-smokers (or ex-smokers stopped 5 years ago), will have no respiratory disease, normal spirometry and be age-matched to the COPD patients.

Asthmatic subjects, either male or female, over the age of 18 with a clinical diagnosis of Asthma with airflow obstruction (FEV1/FVC<0.7).

Capable of giving informed consent.

(ii) Exclusion Criteria

As a result of the medical interview, physical examination or screening investigations, the Physician Responsible considers the volunteer unfit for the study.

Oral corticosteroids taken within last month, as this can affect the breathing response and signifies that their condition needs to be controlled better.

Current involvement (or involvement in the last 4 weeks) in clinical trials assessing investigational medicinal products.

Previous adverse reaction to short or long acting β 2 agonist.

Any subject with a contraindication to taking inhaled beta-2 adrenoceptor agonists (especially Salbutamol) as listed in the British National Formulary will not be entered into this study.

Those who have experienced an acute respiratory exacerbation requiring emergency room treatment and/ or hospitalisation within last four weeks as this signifies that their condition needs to be controlled better.

Pregnant or breast-feeding women.

Subjects unable to give Informed Consent.

7. Study Plan and Treatments (see also 'FLOWCHART')

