An independent scientific investigator will create a computer generated randomisation lists for the study in accordance with the protocol. Code break envelopes will be provided with copies of the randomisation code, which will be stored in the RBH Pharmacy.

11. Sample Size and Statistical Analysis

Determination of sample size

Aerosol deposition. Based on penetration index (PI) data from my previous particle-size deposition study [27], n=12 subjects will have 97% power (1- β) to detect a clinically relevant difference in means of 0.19 for PI, assuming a standard deviation of differences of 0.15, using a paired t-test with a 0.05 two-sided significance level (α). We do not have previous within patient repeatability data for PI for each individual particle size, as it is unethical to expose patients to more radioactivity than is needed. However, our data were highly significant ($p < 0.001$) in differences of PI between the three particle sizes (1.5-, 3-, 6- μm) that correlated with clinically significant differences in bronchodilator responses, and we have used the within subject SD data for PI (collectively of all 3 particles given to each patient), in the sample size calculation.

Small airway physiology. Based on Sacin and Scond data [Verbanck 1999], where MBNW responses in COPD and asthma were measured before and after pMDI salbutamol (corresponding to ΔFEV_1 19% - a clinically important difference), we calculate n=14 subjects will have 90% power (1- β) to detect a clinically relevant difference in means of 0.027 for Scond, assuming a standard deviation of differences of 0.022, using a paired t-test with a 0.05 two-sided significance level (α). Allowing for inherent biological variability for repeated measures over time, the reported intraclass correlation of Scond and Sacin is

Short title: Drug Lung Deposition in COPD

Protocol Version: 1.0; Date 20/10/2011;

Sponsor Ref: NIHR CDF

Page 9 of 14

NRES REC Ethics Number: 12/LO/0004

Eudra CT: 2011-005544-10

0.84, 0.95 respectively [Verbanck 1999], and so the sample-size required for airway physiology analysis in COPD patients is n=26 (Stata-10, Statacorp, Texas, USA).

Statistical methods

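### Lung PHYSIOLOGY sample size: on the printed inputs n=14 has 98.8% power, not 90%, and the intraclass-correlation step to n=26 has no stated formula and does not suit a paired contrast

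*Combined protocol and SAP*

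**What the plan says.** Section 11 (Determination of sample size, small airway physiology) draws on published data in which "MBNW responses in COPD and asthma were measured before and after pMDI salbutamol". From these it states "we calculate n=14 subjects will have 90% power" to "detect a clinically relevant difference in means of 0.027 for Scond, assuming a standard deviation of differences of 0.022, using a paired t-test", at a two-sided 0.05 level.

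A second step follows. It is introduced as "Allowing for inherent biological variability for repeated measures over time", cites intraclass correlations of 0.84 for Scond and 0.95 for Sacin, and concludes "and so the sample-size required for airway physiology analysis in COPD patients is n=26". The software is named. No formula, inflation factor, revised SD or resulting power is given.

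Section 5 carries the result into recruitment: "26 mild-moderate COPD patients". Section 4 names both Sacin and Scond as primary endpoints of this study. The Statistical methods part of section 11 plans paired t-tests with a Bonferroni adjustment for comparisons among the three particle sizes. Section 3 sets the spacing of visits: "There will be an interval of at least 5 days between each study visit".

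**The concern.** The plan prints every input to its first step, so 90% power at n=14 can be checked directly, and it does not follow from them. A gap this large suggests that one input is mislabelled or that a formula other than the stated one was used.

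The second step raises the sample size by 12 patients on the strength of high intraclass correlations. In a crossover, where each patient is his or her own control, high within-patient correlation normally reduces the number needed.

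This paragraph is the only numerical basis for enrolling 26 COPD patients in the study. At stake is whether a reader can tell what those 26 patients are able to detect in the analysis that is planned.

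**Working it through.** **Inputs (section 11).** Scond difference d = 0.027; SD of differences s = 0.022; paired t-test; two-sided alpha 0.05; stated n = 14 at 90% power; intraclass correlations 0.84 (Scond) and 0.95 (Sacin); final n = 26.

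**Method.** Paired t-test power from the noncentral t distribution with n − 1 degrees of freedom and noncentrality (d/s)·√n.

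**Check of the method on the plan's other calculation.** For the deposition study (n = 12, difference 0.19, SD of differences 0.15) the noncentrality is (0.19/0.15)·√12 = 4.388 and power is 97.8%. The plan states 97%. The method agrees with the plan there.

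**Step 1: the plan's figure for n = 14.** d/s = 0.027/0.022 = 1.227. Noncentrality = 1.227·√14 = 4.592. The critical value on 13 degrees of freedom is 2.160. Power is 98.8%, against the stated 90%.

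**Step 2: rounding.** With d between 0.0265 and 0.0275 and s between 0.0215 and 0.0225, power at n = 14 runs from 98.2% to 99.3%. Rounding is not the explanation. For exactly 90% at n = 14, the SD of differences would have to be 0.0288, which is 1.31 times the printed value.

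**Step 3: where 14 may come from.** Two calculations return it.

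- The normal formula for two independent groups, with 0.022 as the SD of one measurement: 2·[0.022·(1.960 + 1.282)/0.027]² = 13.95, so 14 per group.
- A paired t-test at alpha 0.05/6, which has 90.6% power at n = 14.

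The first contradicts the printed test and SD label. The second contradicts the printed alpha. Which one was used, if either, is inference.

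**Step 4: from 14 to 26.** 14 × (1 + 0.84) = 25.76, which rounds up to 26. This is the design effect 1 + (m − 1)·ICC with m = 2, the inflation used for clustered observations. The plan does not state it. For a paired contrast the correlation acts in the other direction: the SD of the difference is s₁·√[2(1 − ICC)], where s₁ is the per-measurement SD. With s₁ = 0.022 and ICC = 0.84 this is 0.022·√0.32 = 0.0124, which is below 0.022.

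**Step 5: what 26 patients deliver for a Scond difference of 0.027.** The second row takes 0.022 as a per-measurement SD with uncorrelated repeats, so the SD of differences is 0.022·√2 = 0.031.

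| SD of differences | alpha 0.05 | alpha 0.05/6 |
|---|---|---|
| 0.022 (as printed) | over 99.9% | 99.9% |
| 0.031 | 98.9% | about 93% |

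The divisor 6 assumes three size pairs for each of two primary indices; the plan does not give the count. With three size pairs only (alpha 0.05/3) and SD 0.022, the between-size Scond difference detectable with 90% power at n = 26 is 0.0168.

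**The case against.** The strongest reply is that nothing of consequence follows. Enrolment is 26, not 14, and Step 5 shows ample power for 0.027 on the printed SD. Even the most plausible mislabelling leaves about 93% at a strict alpha. That stands, and it makes this a correction of the text and not a challenge to the size of the study.

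It can also be said that the second step has a stated purpose, namely variation over time. The source data are before-and-after responses, whereas the treatments are compared across visits at least 5 days apart. An allowance for between-visit variation is reasonable in principle. This stands too, but the allowance has to enter as a larger SD of differences with a source, and none is given. For 26 to be the 90% requirement at alpha 0.05, that SD would have to be about 0.041.

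The target is also open to defence. The plan links 0.027 to a 19% change in FEV1 that it calls clinically important, and such a difference can serve as the target for any contrast. Whether particle sizes differ by that much cannot be settled from the documents.

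A reader might infer from Step 1 that 10 patients would be enough, since n = 10 has 93.1% power on the printed inputs. The documents do not support using that as the correction. It holds only at the unadjusted 0.05 level and only if 0.022 is truly an SD of differences. At 0.05/3, n = 10 has 80.3% power.

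**Conclusion.** The stated power is wrong as written: 98.8% and not 90% at n = 14, given a paired t-test, a difference of 0.027, an SD of differences of 0.022 and two-sided 0.05. The step to 26 is unsupported. No formula is given, and the one simple route found to that number is not valid for a within-patient comparison.

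A reader might conclude that the study is underpowered. The documents do not show this. For Scond at 0.027, the error on the printed inputs makes the study larger than needed. That reassurance rests on 0.022 being either an SD of differences or a per-measurement SD with repeats no worse than uncorrelated. A larger between-visit SD would weaken it, but the documents give no figure for one.

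The absence of a difference and SD for Sacin, and of the number of Bonferroni comparisons, is missing detail and not an arithmetic error. It does mean that nothing can be said about power for Sacin. The point should be fixed because a sample-size statement the trial relies on cannot be reproduced and the correction is cheap.

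**What to change.** Keep enrolment at 26 and rewrite the small airway physiology paragraph of section 11.

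- (a) Confirm whether 0.022 is an SD of differences or a per-measurement SD, and correct the n and power accordingly. If the printed label is right, n = 14 has 98.8% power.
- (b) Remove the intraclass-correlation inflation, or replace it with an explicit between-visit SD of differences, its source and the formula in which it is used.
- (c) State the number of Bonferroni comparisons, and then what 26 patients deliver at that alpha: either the power for 0.027 or the detectable between-size Scond difference. An example of the form is 0.0168 with 90% power at alpha 0.05/3 and SD 0.022, where the divisor 3 assumes three size pairs.
- (d) Say that the calculation covers Scond only.

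The cost is protocol wording. The sponsor must confirm the meaning of 0.022, supply the comparison count and, if the allowance for variation over time is kept, supply the between-visit SD. No change to enrolment, visits or treatments is needed.

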Longitudinal analysis of paired-data will be performed within and between different groups. Data from the primary and secondary endpoints will be used to test the null hypothesis using two-way parametric analysis of covariance (ANCoVA), with factors for subject, treatment period and order. Modified paired t-tests will be undertaken using the Bonferroni method to adjust for P values and multiple comparisons between the three particle sizes. Lung deposition comparisons will be made to assess particle size deposition effects within diseased COPD patients, within healthy subjects (HS) and between disease (COPD) and health (HS). Comparisons will be made to determine the effects of inhalation flow on regional lung deposition of the three particle sizes in COPD and HS. Small airways physiology comparisons will be made between monodisperse aerosols of different particle size in COPD patients and between monodisperse and polydisperse-MDI aerosols.

12. Adverse Events

An **adverse event** (AE) is the development of an undesirable medical condition or the deterioration of a pre-existing medical condition following or during exposure to a pharmaceutical product, whether or not considered causally related to the product. An undesirable medical condition can be symptoms (e.g., nausea, chest pain), signs (e.g., tachycardia, enlarged liver) or the abnormal results of an investigation (e.g., laboratory findings).

In clinical studies, an AE can include an undesirable medical condition occurring at any time, including run-in or wash-out periods, even if no study treatment has been administered.

A **serious adverse event** (SAE) is an AE occurring during any study period (i.e., run-in, treatment, wash-out, follow-up), and at any dose of the investigational product, comparator or placebo, that fulfils one or more of the following criteria:

- results in death
- is immediately life-threatening
- requires in-patient hospitalisation or prolongation of existing hospitalisation
- results in persistent or significant disability or incapacity
- is a congenital anomaly or birth defect
- is an important medical event that may jeopardise the patient or may require medical intervention to prevent one of the outcomes listed above

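### A cheap improvement, not an error: within each set of three particle-size comparisons, Shaffer's step-down rule keeps the 5% family error of plain Bonferroni, never rejects less, and has more power

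*Combined protocol and SAP*

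**What the plan says.** Section 11 (Statistical methods) plans an analysis of covariance with factors for subject, treatment period and order. It then adds: "Modified paired t-tests will be undertaken using the Bonferroni method to adjust for P values and multiple comparisons between the three particle sizes". No step-down or closed procedure is mentioned, and the word modified is not explained.

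The sample-size part of Section 11 sizes the deposition study on one unadjusted comparison. It claims that "n=12 subjects will have 97% power" when mean PI differs by 0.19 and the SD of the paired differences is 0.15. The calculation was done "using a paired t-test with a 0.05 two-sided significance level", with no allowance for three comparisons. The pair of sizes that the 0.19 describes is not named. Section 5 sets recruitment as "Lung DEPOSITION study: 12 mild-moderate COPD patients, 12 healthy subjects". Section 4 makes PI the primary endpoint of that study.

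**The concern.** Bonferroni holds all three pairs at 0.0167 whatever the data show. With three means this is stricter than a 5% family error requires, because the three null hypotheses are logically linked: once one of them is false, at most one of the other two can be true.

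The surplus strictness has a cost here. The study was sized at 0.05 but will be tested at 0.0167, so the analysis has less power than the calculation reports. The groups are small. Question Q2 in Section 2 asks for a specific particle size for optimal deposition, and answering it depends on separating neighbouring sizes (1.5 from 3 micron, 3 from 6 micron), which are the harder comparisons if PI changes steadily with size.

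**Working it through.** **Inputs.** From Section 11: n = 12, difference 0.19, SD of differences 0.15, two-sided 0.05, paired t-test. Three sizes give three pairs, so the Bonferroni level is 0.05/3 = 0.0167.

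**1. The plan's own figure.** Noncentrality = (0.19/0.15) × √12 = 4.39 on 11 df. At two-sided 0.05 the critical value is 2.201 and the exact noncentral-t power is 97.8%. The stated 97% is reproduced to within a point.

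**2. The same inputs at the Bonferroni level.** The critical value becomes 2.820 and the power 91.9%.

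**3. Why Shaffer's rule controls the family error.** If any two of the three equalities of means hold, so does the third. The only joint null is therefore that all three are equal.
- All three equal: a false claim requires the smallest p-value to pass 0.05/3, which has probability at most 5%.
- Exactly one equality true: only that pair can be falsely rejected, and never at a level above 0.05.
- No threshold is below 0.05/3, so every Bonferroni rejection is kept.

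**4. Simulation.** 400,000 trials per setting, three sizes per participant, every pairwise SD of differences 0.15, paired t-tests on 11 df.

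| PI steps (1.5 to 3, 3 to 6 micron) | Quantity | Bonferroni | Holm | Shaffer |
|---|---|---|---|---|
| 0.19, 0.19 | each adjacent pair | 91.9% | 97.8% | 97.8% |
| 0.19, 0.19 | all three pairs | 84.0% | 95.6% | 95.6% |
| 0.19, 0 | the adjacent pair that differs | 91.9% | 94.3% | 96.5% |
| 0.095, 0.095 | each adjacent pair | 31.5% | 42.6% | 50.6% |
| 0, 0 | any false claim | 4.5% | 4.5% | 4.5% |
| 0, 0.19 | false claim on the equal pair | 1.6% | 4.5% | 5.0% |

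The first two rows imply 0.19 + 0.19 = 0.38 between 1.5 and 6 micron. The fourth takes 0.19 as the whole range. No Bonferroni rejection was lost under Shaffer in any setting.

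**5. If the modified t-tests use the pooled error of the model.** With equal variances and (3 − 1) × (12 − 1) = 22 error df, before period terms, the critical values are 2.591 at 0.0167 and 2.074 at 0.05. With two steps of 0.19, adjacent-pair power is 95.5% under Bonferroni and 98.7% under Shaffer.

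**6. If 0.15 is a per-measurement SD.** Section 11 calls 0.15 an SD of differences but also says "we have used the within subject SD data for PI (collectively of all 3 particles given to each patient"). If it were the SD of single measurements, the SD of differences would be 0.15 × √2 = 0.212. With two steps of 0.19, adjacent-pair power would then be 61.8% under Bonferroni and 80.5% under Shaffer.

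**7. Physiology study.** With the Scond inputs of Section 11 (difference 0.027, taken here at each step; SD of differences 0.022) and 26 COPD patients, both rules exceed 99.9%. No useful gain is shown there.

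**The case against.** The strongest reply is that nothing is wrong. Bonferroni is pre-stated, valid and simple, and at two steps of 0.19 it still finds each adjacent pair 92% of the time. That stands. A reader might infer that the plan's method is faulty, or that it generally misses adjacent sizes at the design effect; the documents support neither.

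The power gain also rests on assumptions that the plan does not state. It gives one difference and no pair, and it does not define its modified t-test. Both points stand, and they change the size of the gain but not its direction.

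It is also tempting to say that Bonferroni's extra strictness buys nothing. It does buy something. When one pair is truly equal, its error rate is 1.7% under Bonferroni and can reach 5% under Shaffer. Bonferroni also comes with matching simultaneous intervals.

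Finally, the deposition study has two flows and two groups, hence four sets of three comparisons. With one true null in each set, and treating the sets as independent (an approximation, since the same participants inhale at both flows), the chance of at least one false claim is 1 − (1 − 0.0167)⁴ = 6.5% under Bonferroni and up to 1 − 0.95⁴ = 18.5% under Shaffer. This is a fair cost to name. It does not rescue Bonferroni as a study-wide safeguard, because an adjustment over three sizes does not formally cover flows, groups, doses or endpoints either.

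**Conclusion.** The point holds as an optional gain in efficiency. Within one set of three particle-size comparisons, Shaffer's rule dominates plain Bonferroni: same 5% family limit, no rejection lost, more power. That part is a matter of logic and needs no assumption about effect sizes.

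The amount does depend on assumptions. For PI with 12 participants it is about 6 points per adjacent pair with two steps of 0.19, between 4 and 5 points if only one step is real, about 19 points if 0.19 is the full range in equal steps, and about 3 points with two steps of 0.19 and a pooled error. A reader might take 92% to 98% as following from the plan's inputs alone. It does not, since it requires a difference of 0.38 between the extreme sizes, which the plan nowhere states.

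**What to change.** In Section 11 (Statistical methods), replace the reference to the Bonferroni method by wording such as: within each set of three particle-size comparisons, Shaffer's step-down rule will be used (smallest of the three p-values against 0.05/3; if significant, the other two against 0.05). Holm is an acceptable simpler choice; it gains less when the steps are uneven or small.

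Add that the 5% control applies to each set separately and does not extend across flows, groups, doses or endpoints. Report ordinary 95% intervals, labelled as unadjusted, beside the adjusted p-values, and note that the two can disagree.

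The change costs a few sentences, made before unblinding, and needs no further participants, visits or radiation. What is given up is the set of simple matching simultaneous intervals and some of Bonferroni's slack on a single true null.

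### Lung DEPOSITION study: the penetration index is tied to particle size without a deciding pair, flow or group, and no multiplicity adjustment is stated for the planned flow and COPD-versus-healthy comparisons.

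*Combined protocol and SAP*

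**What the plan says.** Section 4 (Study Outcomes) states: "The primary endpoint for aerosol deposition is penetration index (PI) calculated from planar-images". It adds that PI is to show how regional deposition differs by particle size. It does not say which sizes are compared, at which flow or in which group.

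Under sections 3 and 7, PI comes from the six radiolabelled treatments: 1.5, 3.0 and 6.0 micron, each inhaled SLOW and FAST. Section 5 sets 12 COPD patients and 12 healthy subjects.

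Section 11 (Statistical methods) then plans three kinds of comparison:

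- **Size and disease:** "Lung deposition comparisons will be made to assess particle size deposition effects within diseased COPD patients, within healthy subjects (HS) and between disease (COPD"; the sentence goes on to name healthy subjects as the other side of the disease contrast.
- **Flow:** "Comparisons will be made to determine the effects of inhalation flow on regional lung deposition of the three particle sizes in COPD and HS".
- **Multiplicity:** "Modified paired t-tests will be undertaken using the Bonferroni method to adjust for P values and multiple comparisons between the three particle sizes".

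The model is an ANCoVA with factors for subject, treatment period and order. Flow and disease group are not among the listed factors. The section gives no testing hierarchy, no gate and no exploratory label. The sample-size paragraph rests on one comparison, "using a paired t-test with a 0.05 two-sided significance level", and again names no pair, flow or group.

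**The concern.** A single primary variable does not fix a single primary test. PI by size can be examined at SLOW, at FAST or averaged over flow, and in COPD, in healthy subjects or in both. These analyses can disagree: a size effect might appear at FAST but not SLOW, or in healthy subjects but not in COPD. As written, the choice of which one answers the primary question can be made after the data are seen.

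The flow and COPD-versus-healthy comparisons use the same endpoint and address principal research questions (Q2 and part of Q1 in section 2), yet no adjustment is stated for them. A real size effect, which the sponsor's earlier data suggest, would not protect them. At stake is whether a reported flow or disease difference in PI, from 12 subjects per group, can be taken as more than a chance finding among many.

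**Working it through.** **1. The plan's own figure.** Section 11 says "n=12 subjects will have 97% power" for a "difference in means of 0.19 for PI, assuming a standard deviation of differences of 0.15". The standardised difference is 0.19/0.15 = 1.267, so the noncentrality is 1.267 × √12 = 4.39 on 11 degrees of freedom. Power at two-sided 0.05 is 97.8%, which agrees with the stated 97% to within a point. That power belongs to one unadjusted test.

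**2. How many tests the text could cover.** The documents give no count. Crossing 3 sizes, 2 flows and 2 groups in full gives:

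| Comparison | Count | Stated adjustment |
|---|---|---|
| Size pairs within group and flow | 3 × 2 × 2 = 12 | Bonferroni between sizes |
| SLOW v FAST within size and group | 3 × 2 = 6 | none |
| COPD v healthy within size and flow | 3 × 2 = 6 | none |
| Total | up to 24 | |

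**3. Flow tests at 0.05, no true flow effect.** With independent visit errors, the contrasts at different sizes or in different groups share no data once the subject effect cancels, so they are independent.

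- COPD only: 1 − 0.95³ = 14.3%.
- Both groups: 1 − 0.95⁶ = 26.5%.

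Allowing a subject-by-flow component lowers the two-group figure to 23-25%.

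**4. Flow and disease tests together.** The disease contrasts are correlated through the subject effect, so simulation is needed. I assumed 12 per group, 20,000 trials per setting, and a within-subject correlation of 0 to 0.9, because the documents do not give one. The six disease tests at 0.05 carry 11-26%. Flow and disease tests together carry 35-42%. These figures do not depend on the size null. In a check with a between-subject SD of 0.10 and a visit-error SD of 0.15/√2, the joint figure was about 40% both with no size effect and with a true size difference of 0.19.

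**5. Size tests, no true size effect.** One Bonferroni family of three, each test at 0.05/3 = 0.0167, has a simulated error of 4.3-4.9%. The total depends on how the family is read:

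| Reading of the Bonferroni rule | Risk of at least one false positive |
|---|---|
| Three tests per flow and group (four families) | 16.4-17.6%; check 1 − 0.955⁴ = 16.8% |
| As above, behind an omnibus test in each family | about 12% |
| Size averaged over flow (two families) | about 9%; check 1 − 0.955² = 8.8% |
| Bonferroni over all 12 size tests | 4.5-4.9% |

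**6. Everything together, no effect of any kind.** With size tests at 0.05/3 and the rest at 0.05, all 24 tests give 42-47% by simulation. Treating them as independent gives 1 − (1 − 0.05/3)¹² × 0.95¹² = 55.8%. A leaner reading (size averaged over flow, 6 flow tests, 3 disease tests averaged over flow) still gives 38-41%.

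**7. Power for a 0.19 difference at n = 12.** The noncentrality is 4.39 throughout. Power is 91.9% at 0.05/3, 75.7% at 0.05/12 and 64.5% at 0.05/24.

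**The case against.** The strongest reply is that the plan is tighter than a full crossing suggests. Section 4 ties the primary endpoint to particle size, and the stated purpose concerns COPD patients. The Bonferroni rule gives no family size, so it could span every size comparison. The ANCoVA is listed before the t-tests, so an omnibus-then-pairwise sequence is plausible. Flow (Q2) is posed as a separate question from size and disease (Q1), and controlling error per question is defensible in a small mechanistic crossover.

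Much of this stands, and it rules out some stronger readings:

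- A reader might infer that any of 24 tests could be reported as the primary result. Flow-only and disease-only contrasts do not fit the primary endpoint as section 4 words it. The ambiguity there concerns the size pair, the flow and the group.
- A reader might take 24 as the planned number of tests. It is a derived upper count.
- A reader might take 17% as the error of the size tests. It is one reading among several, and it assumes no size effect, although section 11 reports earlier differences between these same sizes at p<0.001.

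The reply does not reach the flow and disease comparisons. No stated rule covers them. Counting error separately for flow still leaves 14% in COPD and about 26% over both groups. An omnibus gate is nowhere stated, and the listed model factors include neither flow nor disease group. The protocol does not label these comparisons exploratory.

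**Conclusion.** The point holds, and its weight falls on the flow and disease comparisons. If there is no flow or disease effect, testing flow at 0.05 carries about a 14% false-positive risk in COPD and 26% in both groups. Flow and disease tests together carry about 35-42%, whether or not particle size matters. The size tests carry from under 5% to about 17% on their own, according to the reading. With no effects at all and up to 24 tests, the simulated total is about 42-47%; this is not a ceiling, since independence would give about 56%.

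The figures assume 12 completers per group, the full crossing of sizes and flows, 0.05 for each comparison with no stated adjustment, and within-subject correlations that the documents do not supply. The endpoint itself is sound. The defect is that the test deciding the primary question is not fixed in advance and that comparisons beyond size are unprotected. It should be corrected before analysis.

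**What to change.** In section 11, name one primary family for PI and label the rest. One suitable choice is the three Bonferroni-adjusted comparisons of 1.5, 3.0 and 6.0 micron at SLOW flow in the 12 COPD patients. It fits the paired calculation at n = 12, and SLOW is the flow used throughout the Lung PHYSIOLOGY study. Family error is about 4.5%. Power for a pair that truly differs by 0.19 is 92% at 0.05/3, and this should replace the 97%. Another family would serve equally well if named beforehand. All other size, flow and COPD-versus-healthy comparisons of PI would be labelled exploratory and reported as estimates with 95% confidence intervals.

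Two alternatives are weaker. Bonferroni over all 24 tests controls error but cuts power to 64.5%. A fixed sequence of families (size at SLOW then FAST in COPD, size in healthy subjects, flow, disease) needs a definition of success at each step:

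- If any rejection opens the next step, and two sizes are equal while the third differs by 0.19, simulated family error is about 9%.
- If all three rejections are required, and 1.5 and 6.0 micron differ by 0.19 with 3.0 midway, only about 6% of trials pass the first step.

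The cost is one paragraph, with no added patients or procedures. The downside is that flow and COPD-versus-healthy results (Q2 and part of Q1) could not be claimed as confirmatory.
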